8.1.9 Visit 6 (Day 197~242) –3rd Vaccination

The following procedures will only be performed on subjects who agreed to have 3rd vaccination. The Visit 5 and Visit 6 could be the same day.

- (1) Collect informed consent form for vaccine group who agreed to have 3rd vaccination.**
- (2) Check contraindication for the third vaccination and the possibility of delay vaccination**
- (3) Conduct physical examination.**
- (4) Measure vital signs.**
- (5) Perform a urine pregnancy test.**
- (6) If subject encountered \geq Grade 3 hypertension, subject should be checked the existence or deterioration of proteinuria or other renal damage sign.**
- (7) Collect blood sample for following tests:**
 - **Immune response assessments**
 - **Blood routine tests**
 - **Biochemistry test**
 - **Immunology test**
 - **T cell function (optional)**
- (8) Perform 3rd vaccination**
- (9) Observe closely during vaccination and at least 30 minutes after vaccine administration for the change of vital sign or acute anaphylactic event at site by site staff.**
- (10) Instruct the subject to monitor body temperature and complete self-evaluation e-diary correctly.**

(11) Review concomitant medications.

(12) Conduct COVID-19 surveillance

(13) Record and report adverse event, serious adverse event, or any symptoms of COVID-19 if any has occurred since the previous visit.

8.1.10 Safety call on 7 days after Visit 6 (Only for subjects who have 3rd vaccination)

Safety calls on 7 days after Visit 6 to monitor subjects' unsolicited AEs and symptoms of COVID-19. Call should be inquired the phenomenon of allergic skin reaction, especially itching and redness, or other unsolicited allergy reaction. No matter injection site or extending to other body site, site staff should arrange unscheduled visit to verify the allergic reaction and check HLA typing if indicated.

8.1.11 Follow up on 14 days after Visit 6 (\pm 3 day) (Only for subjects who have 3rd vaccination)

(1) Conduct physical examination.

(2) Measure vital signs.

(3) If subject encountered \geq Grade 3 hypertension, subject should be checked the existence or deterioration of proteinuria or other renal damage sign.

(4) Collect blood sample for following tests:

➤ **Immune response assessments**

➤ **Blood routine tests**

➤ **Biochemistry test**

➤ **Immunology test**

➤ **T cell function (optional)**

(5) Review concomitant medications.

(6) Conduct COVID-19 surveillance

(7) Record and report adverse or serious adverse event.

8.1.12 Day 253 and Day 309- Bi-monthly Safety calls

After Day 197, subjects will enter the **long-term follow-up** with a safety call bi-monthly on Day 253 and Day 309 to monitor subjects' unsolicited AEs and symptoms of COVID-19.

8.1.13 Long-term follow-up (Day 365 \pm 45 days)

(1) Measure vital signs.

(2) If subject encountered \geq Grade 3 hypertension, subject should be checked the existence or deterioration of proteinuria or other renal damage sign.

(3) Collect blood sample for following tests only for subjects **have 2 vaccinations** in lot-to-lot consistency /immunogenicity group:

- Immune response assessments

(4) Collect blood sample for following tests only for subjects have 3rd vaccination:

- Immune response assessments

- (5) Record adverse events, including AESI, MAAE, SAE, or any symptoms of COVID-19 if any has occurred since the previous visit.

8.2 Early Termination (ET)

For subjects in lot-to-lot consistency/immunogenicity group who discontinue this study earlier, a final follow-up may be arranged not **later** than 7 days and all study procedures listed for Visit 5 should be completed.

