All subjects will come back on Day 197, Visit 5, for immunogenicity persistence check in immunogenicity group and safety check for safety group. **Once subject completes Visit 5, he or she will be unblinded. Subjects received placebo will withdraw from the study and subjects who received UB-612 vaccine will be invited to join the extension study to determine the durability of the immune response and long-term safety after unblinding. Meanwhile, subjects in vaccine group will be encouraged to have a third dose of UB-612. All subjects who received UB-612 vaccine will be followed up for 12 months.**

All subjects will receive safety calls on Day 8, Day 15, Day 22, Day 36, Day 43, Day 64, Day 71, Day 78, Day 85, Day 253, and Day 309 that will serve both to monitor for unsolicited AEs or/and to monitor for symptoms of COVID-19. After Day 57, each week (i.e., every 7 days) the subject will receive a prompt on their smartphone device to regularly surveillance for signs and symptoms of COVID-19 and SAE. **Subjects who received 3rd dose of UB-612 will receive an extra safety call on 7 days post 3rd vaccination.**

If a Grade 3 local reaction, systemic event, or fever are reported in the reactogenicity e-diary, a telephone contact should occur to ascertain further details and determine whether a site visit is clinically indicated. If suspected Grade 4 local reaction systemic event and /or fever is reported in the reactogenicity e-diary, a site visit should occur to confirm whether the event meets the criteria for Grade 4. All subjects were encouraged to contact site staff once they encountered Grade 3/4 AE. Allergic skin reaction should be monitored for 14 days post vaccination and should be contacted regardless of severity.

If a subject experiences a febrile illness associated with respiratory symptoms, he or she is instructed to contact the site immediately. Subjects may utilize a COVID-19 illness e-diary to prompt him/her to report any symptoms.

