7.4.7 Blinding

This is an observer-blind study, as the physical appearance of the investigational vaccine candidates and the placebo may differ. Only the dispenser(s)/administrator(s) will be unblinded. These study staffs are responsible for receiving, dispensing, preparing and administering the study intervention. The investigational products should be administered in a manner that prevents the subjects to identifying their treatment based on vaccine physical appearance. The dispenser(s)/administrator(s) should not participate in any of the study clinical evaluations or assay, and keep minimum contacts with other study personnel.

Neither the subjects nor the investigators, sponsor staffs, clinical monitors, study coordinators other than dispenser(s)/administrator(s), or other site staff who involve in clinical evaluation of the subjects will be aware of the treatment received either at the time of randomization or later, throughout the conduct of the trial. **These study personnel will be blinded until Visit 5. Unblinding will be carried out via disclosed Randomization Envelop during Visit 5.**

The treatment codes will be not prematurely broken unless an emergency situation, when the appropriate management of the subject necessitated knowledge of the treatment allocation, occurred. In the event of a medical emergency, if possible, the clinical monitor should be contacted before the treatment code blind is broken to discuss the need for unblinding. For unblinding a

subject, the treatment code blind can be obtained by the investigator, by opening the emergency envelope.

The sponsor must be notified immediately if the treatment code blind is broken. The date, time, and reason that the blind is broken must be recorded in the source document and the same information (except the time) must be recorded on the eCRF.

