7.4.8.2 Removal of Subjects from the Study

Subjects may withdraw from the study for any of the following reasons:

- Lost to follow-up
- Consent withdrawal
- Death
- Any pathological event, clinical adverse event, or any change in the subject's status giving indication to the doctor that further participation in the study may not be the best interests of the subject, according to investigator's discretion.
- Study terminated by sponsor

Subjects who withdraw consent will be replaced.

Subjects are free to withdraw from the study at any time without providing reason(s) for withdrawal and without prejudice to further research treatment. The reason(s) for withdrawal will be documented in the case report form (CRF).

Subjects withdrawing from the study, except subject death, will be encouraged to complete the same final evaluations (as Visit 5 procedure) within 7 days after withdrawal, as subjects completing the study according to this protocol, particularly safety evaluations. The aim is to record data in the same way as for subjects who completed the study.

Reasonable efforts will be made to contact subjects who are lost to follow-up (where possible, at least 3 telephone calls). These efforts must be documented in the subject's file.

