8.1.8 Visit 5 (Day 197 ± 15 days) –Unblinding / Early Termination

- (1) Conduct physical examination.
- (2) Measure vital signs.

- (3) If subject encountered \geq Grade 3 hypertension, subject should be checked the existence or deterioration of proteinuria or other renal damage sign.

(4) Unblinding

(5) Withdraw subjects who received placebo

- (6) Collect blood sample for following tests only for subjects in lot-to-lot consistency /immunogenicity group:
- Immune response assessments
- (7) Review concomitant medications.
- (8) Record and report adverse event, serious adverse event, or any symptoms of COVID-19 if any has occurred since the previous visit.

The subject will receive a prompt on their smartphone device to regularly surveillance for signs and symptoms of COVID-19 each week.

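### V-205: the early-termination visit takes over the Visit 5 procedure list, unblinding included, with no exemption and against the emergency-only code-break rule in 7.4.7

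*Supplement*

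**What the plan says.** All references are to the V-205 protocol.

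- **8.1.8** covers two visits under one heading, "Unblinding / Early Termination". Its numbered list has unblinding as step 4, withdrawal of placebo recipients as step 5, and adverse-event recording as step 8. Steps 4 and 5 carry no condition on the study day or the reason for the visit.
- **8.2** sets the early-termination visit: "For subjects in lot-to-lot consistency/immunogenicity group who discontinue this study earlier, a final follow-up may be arranged", no later than 7 days, and at it "all study procedures listed for Visit 5 should be completed".
- **7.4.8.2** covers all withdrawals except deaths. These subjects "will be encouraged to complete the same final evaluations (as Visit 5 procedure) within 7 days after withdrawal".
- **The schedules of assessments** (synopsis and 7.2) label one column both 5/ET and unblinding. They do so for the lot-to-lot/immunogenicity group and for the safety check group.
- **7.4.7** sets the blinding rule: "The treatment codes will be not prematurely broken unless an emergency situation". The same section says "Unblinding will be carried out via disclosed Randomization Envelop during Visit 5".
- **7.1** words the planned unblinding differently: "Once subject completes Visit 5, he or she will be unblinded".

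**The concern.** The trial is observer-blind, and its primary safety endpoints are compared between arms by Fisher's exact test (10.5.1). If the early-termination visit follows the Visit 5 list as written, the code of a subject who leaves at any earlier day is opened without an emergency. Two things are then at risk.

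First, the leaver's last adverse-event and relatedness entries can be made with the arm known. Relatedness is the investigator's judgement (9.5.6.7). It feeds the summaries of related events (10.5) and the stopping rules, which turn on events judged possibly related and ignore placebo data (9.6.1). Leavers still count: the Safety Population takes in everyone vaccinated at least once (10.3), and event follow-up runs until resolution or stabilisation (9.5.5.3). An adverse event is itself a listed ground for withdrawal (7.4.8.2).

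Second, site staff may learn allocations while other subjects are still blinded, under 6:1 block randomization with numbers issued in order (7.4.6).

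**Working it through.** No power or alpha figure is at stake, so the check is a comparison of passages followed by a bound on scale.

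**Passages side by side**

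| Question | Points towards unblinding at early termination | Points against |
|---|---|---|
| Is unblinding part of the visit? | 8.1.8: shared heading, step 4 unconditional; 8.2: all listed procedures; schedules: column 5/ET headed as unblinding | 7.4.8.2 speaks of evaluations, and opening a code is not one |
| Is an early code break allowed? | 7.4.7: unblinding takes place during Visit 5, and 8.1.8 treats early termination as that visit | 7.4.7: premature break in an emergency only; 7.1: only once Visit 5 is completed |
| Does step 5 make sense for a leaver? | No exemption is written | The subject has already withdrawn, so the step has no purpose |
| Who is covered? | 7.4.8.2: all withdrawals except deaths; schedules: both groups | 8.2: lot-to-lot/immunogenicity group only, and the visit is optional |

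The left column can be followed in good faith by a site that treats early termination as Visit 5. In that case the sponsor notification and the record of date and reason, which 7.4.7 attaches to a broken code, might not be triggered. No sentence anywhere settles which column governs.

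**Scale**

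Inputs: 10% drop-out and about 3850 core adults (10.2); 966 adults in the immunogenicity and lot-to-lot group, being 812 young adults and 154 elderly (7.4.6).

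- Group named in 8.2, if 966 is the randomized number: 0.10 × 966 = 96.6, about 97.
- Same group, if 966 is what remains after loss: 966 / 0.90 = 1073.3, rounded up to 1074 randomized; 1074 − 966 = 108.
- All core adults, if every withdrawal attended under 7.4.8.2: 0.10 × 3850 = 385.

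Both readings of 966 are kept. Section 7.4.6 calls these subjects evaluable, while 10.2.2 reaches the 396 vaccinees of the lot comparison after already allowing for drop-out.

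Given 10% drop-out, these are upper bounds. Attendance is optional, some leavers will be lost to follow-up or dead, and some may leave after Visit 5. The documents give no distribution of leaving times, so the share before Day 57 cannot be derived.

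**The case against.** The strongest case on the other side is that the plan never plainly orders early unblinding. Section 7.4.7 forbids it outside emergencies, 7.1 places it after a completed Visit 5, and step 5 is meaningless for someone who has already left, so steps 4 and 5 read as belonging to the scheduled visit. A numbered list need not be an order of execution, and if it were, adverse events would follow unblinding at the scheduled Visit 5 too. Leavers contribute little later data. Reactogenicity is self-recorded in the e-diary, the Day 57 titre is a laboratory result, and planned unblinding is already rolling by subject.

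Much of this stands. A reader might infer that every early leaver is unblinded. The documents do not support that: 8.2 covers one group and says the visit may be arranged, and 7.4.8.2 only encourages it. The defect is a contradiction, not a settled instruction. The main exposure is investigator judgement on unsolicited and serious events, not titres or diary data.

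A reader might also infer a definite number of block-mates exposed. That does not follow either. If one assumes blocks of 7, independent 10% drop-out, full attendance, and staff who know the block boundaries, then 3850 / 7 = 550 blocks and 550 × 0.10 × 6 = 330 vaccinees would be identifiable. With blocks of 14 under the same assumptions, both placebo subjects must leave, and 275 × 0.10² × 12 = 33. Block size is not stated, and nothing says that assessing staff know the boundaries.

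Two parts of the objection fall short. Rolling unblinding is planned for Day 197 ± 15, well after that subject's Day 57 endpoints, whereas an early-termination visit can fall before them. And a good reason to read steps 4 and 5 narrowly is not a written exemption: the shared heading, the instruction to complete all listed procedures and the schedule columns all point the other way.

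**Conclusion.** The concern holds as an internal conflict with a practical consequence. Sections 8.1.8 and 8.2 and the 5/ET schedule columns put unblinding into the early-termination visit without exemption, and 7.4.7 permits a premature code break only in an emergency. A subject who attends such a visit before the Visit 5 window can therefore be unblinded before the final adverse-event and relatedness entries, and staff may learn allocations while others remain blinded.

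The size is bounded by about 97 to 108 adults in the group that 8.2 names, and by about 385 across the core group if all withdrawals attended. Both bounds assume the plan's 10% drop-out. Disclosure to block-mates is possible but cannot be quantified, and neither the direction nor the size of any bias in a primary comparison can be derived from the documents. The point is more than a missing detail, because a written procedure, if followed, opens codes early.

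**What to change.** In 8.1.8, 8.2, 7.4.8.2 and the schedules (synopsis and 7.2), state that:

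1. steps 4 and 5 of the Visit 5 list do not apply at an early-termination visit held before the Visit 5 window;
2. the code stays closed at that visit unless the emergency route in 7.4.7 applies;
3. adverse events and relatedness are recorded before any code is opened. This would also settle the order at the scheduled Visit 5, where 7.1 and 7.4.7 differ.

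The cost is a few words in an amendment and a note to sites, with no change to sample size, visits or analyses. The one downside is that an early leaver learns the allocation later.

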8.3 Unscheduled Visit

Subjects who suffer from Grade 3/4 solicited AE should return to site ASAP for further survey and treatment. All AEs recognised during the unscheduled visits are medically attended adverse events (MAAE), except for confirmed COVID-19 disease.

- If a Grade 3 local reaction, systemic event, or fever is reported in the reactogenicity e-diary, a telephone contact should occur to ascertain further details and determine whether a site visit is clinically indicated.
- If suspected Grade 4 local reaction systemic event or fever is reported in the reactogenicity e-diary, a site visit should occur to confirm whether the event meets the criteria for Grade 4.

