8.1.3 Day 8, 15, and 22 –Safety calls

Safety calls on Day 8, Day 15 and Day 22 to monitor subjects' unsolicited AEs and symptoms of COVID-19. Calls on Day 8 and Day 15 should be inquire the phenomenon of allergic skin reaction, especially itching and redness, or other unsolicited allergy reaction. No matter injection site or extending to other body site, site staff should arrange unscheduled visit to verify the allergic reaction and check HLA typing if indicated.

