9.5.6.4 Definition of Medically Attended Adverse Event

A Medically Attended Adverse Event (MAAE) is an AE with a medically-attended visit that is not a routine visit for physical examination or vaccination, such as visits for hospitalization, an emergency room visit, or an otherwise unscheduled visit to or from medical personnel (medical doctor) for any reason.

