10.5.1 Analysis of Primary Safety Endpoint(s)

- Local reactions for up to 7 days following each dose

Local reactions for up to 7 days following each dose will be summarized with counts and percentages of participants with the indicated endpoint and the associated Clopper-Pearson 95% CIs by study group and each vaccination. The group comparison will be assessed by Fisher's exact test. Summary of descriptive statistics by age group will be also provided.

- Systemic events for up to 7 days following each dose

Systemic events for up to 7 days following each dose will be summarized with counts and percentages of participants with the indicated endpoint and the associated Clopper-Pearson 95% CIs by study group and each vaccination. The group comparison will be assessed by Fisher's exact test. Summary of descriptive statistics by age group will be also provided.

- Unsolicited AEs from Day 1 to Day 57

Unsolicited AEs will be presented by descriptive summary statistics (counts, percentages, and associated Clopper-Pearson 95% CIs) with system organ class and preferred term for each study group. The group comparison will be assessed by Fisher's exact test. Summary of descriptive statistics by age group will be also provided.

- MAAEs and SAEs from Day 1 to Day 365

MAAEs and SAEs will be summarized by counts, percentages, and associated Clopper-Pearson 95% CIs for each study group. The group comparison will be assessed by Fisher's exact test. Summary of descriptive statistics by age group will be also provided. **Additionally, the AESIs and ADEs occurred after third vaccination for subjects received three vaccinations will be also summarized separately.**

- AESIs and ADEs from Day 1 to Day 365

AESIs and ADEs will be summarized by counts, percentages, and associated Clopper-Pearson 95% CIs for each study group. The group comparison will be assessed by Fisher's exact test. Summary of descriptive statistics by age group will be also provided. **Additionally, the AESIs and ADEs occurred after third vaccination for subjects received three vaccinations will be also summarized separately.**

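### V-205 counts adverse events seen at protocol-arranged skin-verification visits as medically attended, so solicited local reactions can leak into the primary MAAE comparison

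*Supplement*

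**What the plan says.** All references are to the V-205 protocol unless stated.

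- **Counting rule, 8.3.** "All AEs recognised during the unscheduled visits are medically attended adverse events (MAAE), except for confirmed COVID-19 disease". Confirmed COVID-19 is the only exception; solicited reactions are not excepted.
- **Definition, 9.5.6.4.** The list of qualifying contacts ends with "an otherwise unscheduled visit to or from medical personnel (medical doctor) for any reason".
- **Visit order after dose 1, 8.1.3.** "Calls on Day 8 and Day 15 should be inquire the phenomenon of allergic skin reaction, especially itching and redness". Then: "No matter injection site or extending to other body site, site staff should arrange unscheduled visit to verify the allergic reaction". No grade is named.
- **Visit order after dose 3, 8.1.10.** The call 7 days after Visit 6 repeats the inquiry ("Call should be inquired the phenomenon of allergic skin reaction, especially itching and redness, or other unsolicited allergy reaction") and the order to arrange a visit.
- **After dose 2, 8.1.5.** The Day 36 and Day 43 calls carry neither the skin inquiry nor the visit order.
- **Solicited reactions, 9.5.5.1.** Table 9-1 grades itching at the injection site and redness as local reactions, Grade 1 included. Table 9-2 grades skin allergic reaction separately.
- **Endpoint and analysis, 6.2 and 10.5.1.** Local reactions, and MAAEs with SAEs to Day 365, are both primary safety endpoints. "MAAEs and SAEs will be summarized by counts, percentages, and associated Clopper-Pearson 95% CIs for each study group", and the arms are compared by Fisher's exact test.

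**The concern.** An MAAE endpoint is useful because attendance stands in for a need for care. That link breaks when the trial itself generates the attendance. Under the rules above, a subject who mentions an itchy arm on the Day 8 call can be brought in, and whatever is recognised at that visit is an MAAE, even if allergy is ruled out and nothing is done.

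Local skin reactions may well be commoner after an adjuvanted vaccine than after saline. If so, part of any difference in MAAEs between arms would be reactogenicity already shown in the local-reaction tables, and a reader could not tell it from a difference in need for care. Unless the reason for each visit is recorded, the two cannot be separated reliably afterwards.

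**Working it through.** **Step 1. Does the text produce the leak?** Follow one case: Grade 1 itching at the injection site, reported on the Day 8 call.

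1. Table 9-1 makes it a solicited local reaction.
2. Section 8.1.3 names itching, includes the injection site and sets no grade, so a verification visit is arranged.
3. The visit is unscheduled. Section 8.3 makes each AE recognised there an MAAE. The same section speaks of solicited AEs, so solicited reactions fall within its term.
4. Section 10.5.1 puts the event into the Fisher comparison of MAAEs.

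No step depends on the subject seeking or receiving care.

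**Step 2. Is the trigger consistent?**

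| Section | Event | Action |
|---|---|---|
| 8.1.3, 8.1.10 | Allergic skin reaction, itching or redness, any site, no grade | Arrange a visit |
| 7.1 | Allergic skin rash, Grade 3/4 | Call first, then judge whether a visit is needed |
| 7.1 | Allergic skin reaction, any severity | Contact |
| 8.3, opening sentence | Solicited AE, Grade 3/4 | Return to site |
| 8.3, first bullet | Local reaction, Grade 3 | Telephone contact decides |
| 8.1.5 (after dose 2) | None named | None |

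Read literally, ungraded itching after dose 1 leads to a visit while a Grade 3 rash leads to a call. The number of protocol-made MAAEs therefore depends on which passage a site follows.

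**Step 3. How large could it be?** The documents state no MAAE figure to reproduce and no itching or redness rate by arm for V-205; Phase I had no placebo group. What follows is illustration only.

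Inputs:
- Arm sizes: 3850 adults at 6:1 (7.4.6) give 3850 × 6/7 = 3300 vaccine and 3850/7 = 550 placebo.
- *b*: proportion with any other MAAE, equal in both arms. Assumed.
- *v*, *p*: proportions with a reaction leading to a verification visit, vaccine and placebo. Assumed.

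Formulas, taking the two sources as independent:
- MAAE proportion, vaccine: V = 1 − (1 − b)(1 − v). Placebo: P = 1 − (1 − b)(1 − p).
- Share of vaccine-arm MAAE subjects counted only through the rule: (V − b)/V.
- Power: two-sided 5% comparison of two proportions, normal approximation, 3300 v 550. Simulated Fisher tests agree closely.

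Example with b = 10%, v = 10%, p = 2%: V = 1 − 0.90 × 0.90 = 19.0%; P = 1 − 0.90 × 0.98 = 11.8%; share = (19.0 − 10.0)/19.0 = 47%.

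| b | v / p | V | P | Share | Power |
|---|---|---|---|---|---|
| 5% | 2% / 1% | 6.9% | 5.9% | 28% | 0.12 |
| 5% | 10% / 2% | 14.5% | 6.9% | 66% | about 1 |
| 10% | 2% / 1% | 11.8% | 10.9% | 15% | 0.08 |
| 10% | 5% / 1% | 14.5% | 10.9% | 31% | 0.63 |
| 10% | 10% / 2% | 19.0% | 11.8% | 47% | 0.99 |
| 20% | 2% / 1% | 21.6% | 20.8% | 7% | 0.06 |
| 20% | 10% / 2% | 28.0% | 21.6% | 29% | 0.89 |

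Other MAAEs are equal in every row, so power here is the chance of a significant difference produced by the visit rule alone. It runs from close to the nominal 5% to near certainty, depending on rates that nobody can read from the documents.

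**Step 4. Direction.** Only the third-dose trigger is one-sided by design: placebo subjects leave at Visit 5 (8.1.8), so 8.1.10 reaches vaccine recipients alone. After dose 1 the direction is inferred, not documented.

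**The case against.** - **The visit is for allergic reactions, and ordinary itching belongs to Table 9-1.** This has weight. The trigger should not be read as any itching or redness whatever. But 8.1.3 names both signs, includes the injection site, and makes the visit the means of finding out whether the reaction is allergic. Once the subject attends, 8.3 counts the event whatever the answer.
- **Other passages put a call first.** They do, for Grade 3 and Grade 3/4 events. They do not withdraw the order in 8.1.3, and the conflict is itself part of the problem.
- **Phase I suggests a large effect.** A reader might cite the 30% with injection site reaction recorded as an unsolicited event. V-123 section 5.5 does not support that use. The figure is from the 10 µg group, and the same section says procedural issues led to some local reactions being logged as unsolicited. At 100 µg, the V-205 dose, the only related unsolicited event was one case of constipation.
- **Nothing is decided on the MAAE test.** Correct. The stopping rules (9.6.1) do not use MAAEs, and they are absent from the endpoints listed for the first four interim analyses (10.9). The harm is to interpretation of a primary safety comparison.
- **A broad definition is conservative, and a Grade 3/4 reaction brought back for treatment is real medical attention.** Both stand. The remedy should not strip all solicited reactions from MAAEs, and should keep the broad count visible.
- **The SAP may deal with it.** No V-205 SAP is shown, and a separate table could be left to it. It can split the events only if the reason for the visit was collected.

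**Conclusion.** The definition and the visit order together let solicited local reactions enter a primary safety endpoint solely because the protocol arranged the visit. That follows from the text and needs no assumed rate.

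The size is unknown. With 10% other MAAEs in each arm, the effect is negligible at assumed visit rates of 2% v 1% (11.8% v 10.9%, power 0.08) and large at 10% v 2% (19.0% v 11.8%, power 0.99). These figures assume 3300 v 550 subjects, equal other MAAEs and independence of the two sources.

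Two stronger readings are tempting. One is that the endpoint turns into a count of local reactogenicity. The documents do not show this: over other MAAEs of 5–20% and vaccine-arm visit rates of 2–40%, the share due to the rule runs from 7% to 88%. The other is that a false excess in the vaccine arm is certain. It is a reasonable inference, but no placebo rate exists to establish it.

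**What to change.** 1. **Collect the reason.** Add an eCRF field for each unscheduled visit: protocol-arranged verification only, or care sought or treatment given.
2. **Define the comparison.** In 8.3, 9.5.6.4 and 10.5.1, make the between-arm MAAE comparison on events with care sought or treatment given. Grade 3/4 reactions that needed treatment stay in.
3. **Show the rest.** Report events attended only at a verification visit in a separate row, by arm, and give the all-visits MAAE count as well, so that no safety information is lost.
4. **Reconcile the triggers.** Sections 7.1, 8.1.3, 8.1.10 and 8.3 conflict on when a call and when a visit is required. They must be brought into agreement; which rule is right is a clinical decision for the sponsor and investigators.

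The cost is one eCRF field, an extra table row and wording changes. No added visits or subjects are needed. Classifying the reason for a visit takes some judgement at the site, which is why the all-visits count should stay in the report.
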